## 9. ASSESSMENT OF SAFETY

#### 9.1. Specification of Safety Parameters

The primary safety measures are subject-evaluated ocular tolerability and AEs. Other safety measures include biomicroscopy, ophthalmoscopy, BCDVA, IOP, subject questionnaire, and systemic safety (as measured by HR and BP). Urine pregnancy tests for females of childbearing potential will also be conducted.

The assessment of safety will be evaluated by:

- Ocular tolerability
- Biomicroscopy of the anterior segment including evaluation of lids, lashes, cornea, conjunctiva, iris, lens, and anterior chamber. Following topical fluorescein administration, the integrity of the cornea should be evaluated by fluorescein staining
- Ophthalmoscopy (direct or indirect) without dilation to evaluate the vitreous and posterior pole
- Best-corrected distance VA
- Intraocular pressure performed with a Tono-Pen or Goldmann Applanation tonometry
- Subject questionnaire
- Heart rate and BP (as per the site's normal equipment and procedures)
- Adverse events

#### 9.2. Assessing, Recording, and Analyzing Safety Parameters

The timing for recording safety parameters may be found in Table 1 and Table 2.

#### 9.3. Adverse Events and Serious Adverse Events

All AEs and SAEs that occur following consent and until the final study visit should be collected and recorded on the AE or SAE eCRF page. Only TEAEs will be summarized (Section 9.3.1).

All AEs/adverse reactions occurring during the study (ie, once the subject has signed the ICF) **must** be documented, regardless of the assumption of causal relationship, on the respective eCRF. All TEAEs/treatment-emergent adverse reactions must be documented from the time the subject receives the study medication until the subject's participation in the study has been completed. If a subject has ongoing AEs/adverse reactions at the time of study completion or discontinuation from the study, the ongoing AEs/adverse reactions **must** be followed up and provided appropriate medical care until the signs and symptoms have remitted or stabilized or until medical assessments have returned to acceptable or pre-study limits.

Documentation of AEs/adverse reactions includes start date and end date, severity, relationship to study medications, action(s) taken, seriousness, and outcome.

#### 9.3.1. Adverse Event Definitions

The following definitions of terms apply to this section:

*Adverse event*. An AE is any untoward medical occurrence associated with the use of a study medication in humans, whether or not it is considered drug related. An AE can therefore be any unfavorable and unintended sign (including abnormal laboratory findings), symptom, or disease temporally associated with the use of the study medication, whether or not related to the study medication. Study medication includes the investigational drug under evaluation and the comparator product or vehicle placebo that is given or administered during any phase of the study.

Medical conditions/diseases present before starting the investigational treatment are only considered AEs if they worsen after starting the investigational treatment. Abnormal test results constitute AEs only if they induce clinical signs or symptoms, are considered clinically significant, or require therapy.

The occurrence of AEs should be sought by open-ended questioning of the subject at each visit during the study. At each clinic assessment/visit, study personnel should ask the following question: "Have you had any problems since your last assessment/visit?" Adverse events also may be detected when they are volunteered by the subject during or between visits or through study assessments.

*Life-threatening adverse event or life-threatening suspected adverse reaction*. An AE or suspected adverse reaction is considered "life-threatening" if, in the view of either the Investigator or Ocuphire, its occurrence places the subject at immediate risk of death. It does not include an AE or suspected adverse reaction that, had it occurred in a more severe form, might have caused death.

*Serious adverse event or serious suspected adverse reaction*. An AE or suspected adverse reaction is considered "serious" if, in the view of either the Investigator or Ocuphire, it results in any of the following outcomes:

- Death
- Life-threatening AE
- Inpatient hospitalization or prolongation of existing hospitalization
- Persistent or significant incapacity or substantial disruption of the ability to conduct normal life functions
- Congenital anomaly/birth defect
- Other medically important serious event

Important medical events that may not result in death, be life-threatening, or require hospitalization may be considered serious when, based upon appropriate medical judgment, they may jeopardize the subject and may require medical or surgical intervention to prevent one of the outcomes listed in this definition.

Treatment on an outpatient emergency basis that does not result in hospital admission, or a hospitalization that is elective or is a preplanned treatment for a pre-existing condition that is

unrelated to the medication under study and has not worsened since the start of the study is not considered an SAE.

*Suspected adverse reaction* means any AE for which there is a reasonable possibility that the drug caused the AE. For the purposes of Investigational New Drug safety reporting, "reasonable possibility" means there is evidence to suggest a causal relationship between the drug and the AE. Suspected adverse reaction implies a lesser degree of certainty about causality than adverse reaction, which means any AE caused by a drug.

Unexpected adverse event or unexpected suspected adverse reaction. An AE or suspected adverse reaction is considered "unexpected" if it is not listed in the IB or is not listed at the specificity or severity that has been observed. "Unexpected," as used in this definition, also refers to AEs or suspected adverse reactions that are mentioned in the IB as occurring with a class of drugs or as anticipated from the pharmacological properties of the drug but are not specifically mentioned as occurring with the particular drug under investigation.

The study medication relationship for each AE/adverse reaction should be determined by the Investigator using these explanations:

- Not related
- Unlikely related
- Possibly related
- Probably related
- Definitely related
- Unknown

Unless the relationship is considered to be "Not related" or "Unlikely related" and there is any valid reason, even if undetermined, for suspecting a possible cause-and-effect relationship between the study medication and the occurrence of the AE, then the AE should be considered "related."

If the relationship between the AE/SAE and the investigational product is determined by Ocuphire to be anything other than "Not related" or "Unlikely related," the event will be considered to be related to the investigational product for the purposes of expedited regulatory reporting.

*Severity* of an AE is defined as a qualitative assessment of the level of discomfort of an AE as is determined by the Investigator or reported to him/her by the subject. The assessment of severity is made irrespective of study medication relationship or seriousness of the event and should be evaluated according to the following scale:

- 1 = Mild: Present, but not distressing, and no disruption of normal daily activity
- 2 = Moderate: Discomfort sufficient to reduce or affect normal daily activity
- 3 = Severe: Incapacitating, with inability to work or perform normal daily activity

A change in severity for a reported AE will require an end date for the previous severity and a new start and end date for the new severity. For example, a change in severity may go from mild

to severe or from severe to moderate. In either case, the start or end times/dates should be recorded.

The term "severe" is used to describe the intensity of an event/reaction; the event/reaction itself may be of relatively minor medical significance (such as a severe headache). This is not the same as a "serious" AE, which is based on a subject/event outcome or action criteria usually associated with events that pose a threat to the subject's life or vital functions. "Seriousness" (NOT severity) serves as a guide for defining regulatory reporting obligations.

Should a pregnancy occur, it must be reported and recorded on the pregnancy form and emailed to \_\_\_\_\_\_, as well as in the eCRF. Pregnancy in itself is not regarded as an AE unless there is a suspicion that an investigational product may have interfered with the effectiveness of a contraceptive medication.

The outcome of all pregnancies (spontaneous miscarriage, elective termination, normal birth, or congenital abnormality) must be followed up and documented even if the subject was discontinued from the study.

Action taken in response to an AE is coded as:

- Dose increased: An indication that a medication schedule was modified by addition; either by changing the frequency, strength, or amount
- Dose not changed: An indication that a medication schedule was maintained
- Dose reduced: An indication that a medication schedule was modified by subtraction, either by changing the frequency, strength, or amount
- Dose interrupted: An indication that a medication schedule was modified by temporarily terminating a prescribed regimen of medication
- Drug withdrawn: An indication that a medication schedule was modified through termination of a prescribed regimen of medication
- Not applicable: Determination of a value is not relevant in the current context
- Unknown: Not known, not observed, not recorded, or refused

Additional other action taken:

- Concomitant medication
- Hospitalization

Outcome of an AE is coded as:

- Fatal: The termination of life as a result of an AE
- Not recovered/not resolved: One of the possible results of an AE outcome that indicates that the event has not improved or the subject has not recuperated
- Recovered/resolved: One of the possible results of an AE outcome that indicates that the event has improved or the subject has recuperated

- Recovered/resolved with sequelae: One of the possible results of an AE outcome where the subject recuperated but retained pathological conditions resulting from the prior disease or injury
- Recovering/resolving: One of the possible results of an AE outcome that indicates that the event is improving
- Unknown: Not known, not observed, not recorded, or refused

In previous clinical studies of Nyxol, the most frequently reported AE was conjunctival hyperemia. Investigators are cautioned to use the appropriate verbatim term on the AE form to describe this observation:

- Redness related to instillation that is transient (ie, is no longer present 2 hours after instillation) = "conjunctival erythema upon instillation"
- Redness that is NOT transient (ie, is present 2 hours after instillation) = "conjunctival hyperemia"

**Expedited reporting of serious and unexpected adverse** events: All SAEs (related and unrelated) will be recorded following subject signature of the ICF consent and until the completion of Visit 5. Any SAEs "suspected" to be related to the study medication and discovered by the Investigator at any time **after** the study must be reported.

Any SAE that occurs must be reported to the CRO within 24 hours of its occurrence or within 24 hours of learning of its occurrence. Recurrent episodes, complications, or progression of the initial SAE must be reported to the CRO as follow-up to the original episode within 24 hours of the Investigator receiving the information. Information about all SAEs will be collected and recorded on the SAE eCRF. All pertinent medical records and information collected during the treatment and follow-up of the subject should be maintained at the site with a copy emailed to \_\_\_\_\_\_\_. The Investigator must assess the SAE relationship and complete the SAE eCRF. The CRO may request additional information. Follow-up information (eg, discharge summary) will be retained in the subject's chart and a copy will be emailed to

In addition, all SAEs should be recorded on the AE eCRF page with the serious question marked "Yes."

It is the Investigator's responsibility to notify the approving IRB of any SAEs on a timely basis, as instructed by Ocuphire following Ocuphire's determination of causality. All subjects who experience an SAE should be followed clinically and undergo the appropriate diagnostic evaluations until stabilization or resolution of the event. Ocuphire will report all SAEs to the FDA on the appropriate schedule, depending if the event is drug related or not drug related, expected, or unexpected (based on the available information in the IB).

Any death occurring during the study and follow-up period must be reported as an SAE. For any death occurring through the end of the study, regardless of the degree of relationship to study medication, the SAE resulting in the death must be reported to the CRO. A death occurring after completion of the study that is not reasonably associated with study medication administration does not require completion of the SAE form.

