#### Limitations of Existing Treatments for Presbyopia

Vuity™ (PCH 1.25%) has recently been approved for the treatment of presbyopia. In two Phase 3 studies, Vuity met its primary outcome measure, with 31% and 26% of Vuity-treated subjects gaining 3 or more lines of mesopic DCNVA 3 hours post-dose compared to 8% and 11% of placebo-treated subjects. However, limitations to Vuity include limited duration of efficacy, with a need for twice daily dosing to achieve efficacy throughout the day; headache, browache, and burning/stinging associated with drug administration; accommodative spasm and risk of angle-closure glaucoma due to activation of the ciliary muscle; and risk of retinal detachment in subjects with high myopia (9).

Other available treatments for presbyopia include reading glasses, bifocals, gradients, bifocal contact lenses, and multifocal intraocular lenses (IOLs). Reading glasses can be inconvenient and must be taken off and put on frequently throughout the day to see objects at far and near distances, respectively. Many patients express frustration with losing or forgetting their reading glasses. Moreover, some patients find glasses unflattering, and contact lenses for presbyopia have their own set of drawbacks regarding eye strain and limitation of use.

A small portion of patients elect surgical intervention, including laser treatment, to achieve monovision. The risks of such interventions include a potential decrease in contrast sensitivity and stereopsis and the creation or worsening of dim light vision disturbances.

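### The SAE definition in Protocol 9.3.1 contradicts itself: it excludes outpatient emergency treatment without exception, although events not requiring hospitalization may be serious on medical grounds.

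*Protocol*

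**What the plan says.** Protocol section 9.3.1 defines an event as serious if, "in the view of either the Investigator or Ocuphire, it results in any of the following outcomes", and then lists the outcomes. Inpatient hospitalization is one of them. Two others do not depend on admission: "Persistent or significant incapacity or substantial disruption of the ability to conduct normal life functions" and "Other medically important serious event".

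The paragraph that explains the last item reads: "Important medical events that may not result in death, be life-threatening, or require hospitalization may be considered serious when, based upon appropriate medical judgment". It goes on to require that the event may put the subject in jeopardy and may need medical or surgical intervention to prevent a listed outcome.

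The next paragraph is a single sentence. It begins "Treatment on an outpatient emergency basis that does not result in hospital admission, or a hospitalization that is elective", continues with preplanned treatment for a pre-existing condition, and ends "unrelated to the medication under study and has not worsened since the start of the study is not considered an SAE". It has no clause saying that an event meeting another criterion is still an SAE.

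The same section ties expedited reporting to the label: "Any SAE that occurs must be reported to the CRO within 24 hours of its occurrence", or of its being learned of.

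**The concern.** An event that needs urgent intervention but no admission is a central case for the medically important criterion. It is also what the first half of the exclusion describes. The criterion is permissive and rests on judgment. The exclusion is categorical and comes after it. A coordinator filling in the seriousness field could reasonably treat the exclusion as the final word.

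Several things depend on that field: the 24-hour report to the CRO, the sponsor's causality determination and the IRB notice that follows it, the sponsor's reporting of SAEs to the FDA, the duty to report suspected related SAEs found after the study (all Protocol 9.3.1), and the summary of serious TEAEs by SOC and PT (SAP 10.1). SAP 7.4.2 states that no safety monitoring committee is planned, so there is no committee review that might catch a mislabelled event.

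**Working it through.** No arithmetic applies. The plan states no figure on this point, and the question is one of wording. The check is to take one type of event and run it through each rule.

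**Test case.** A new event arises after dosing. In the investigator's judgment it may need medical or surgical intervention to prevent a listed outcome. It is treated as an outpatient emergency and the subject is not admitted.

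| Rule or reading (Protocol 9.3.1) | Result for the test case |
|---|---|
| Medically important item and its explanatory paragraph | May be serious; hospitalization not required |
| Exclusion, read literally | Not an SAE, whatever other criterion is met |
| Exclusion, read as a limit on the hospitalization criterion only | No effect; the medically important criterion decides |
| Exclusion, with the closing qualifier (pre-existing, unrelated, not worsened) applied to both halves | No effect on a new event; the medically important criterion decides |

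**Does the text choose among the three readings of the exclusion?**

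1. The limiting reading is sensible, because the sentence pairs an emergency visit with an elective admission and both bear on what counts as hospitalization. But the sentence does not mention the hospitalization criterion. It says the thing described is not an SAE.
2. The shared-qualifier reading strains the grammar. The qualifier follows the hospitalization clause, and the outpatient clause is set off before it by a comma and the word *or*.
3. The literal reading follows the words but contradicts the paragraph immediately before.

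Sections 9.3, 9.3.1 and 9.3.2 of the protocol and section 10 of the SAP contain nothing that ranks the two rules. The wording leaves the conflict open.

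**What changes if a site takes the literal reading?**

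- Lost: the 24-hour CRO report and the regulatory steps that follow from SAE status, and the event's place in the serious-TEAE table.
- Kept: the AE record, including severity, relationship and the seriousness field (Protocol 9.3); follow-up of events ongoing at study end (Protocol 9.3); a count in the TEAE tables by SOC and PT, by severity and by relationship (SAP 10.1); and a row in the AE listing, flagged non-serious (SAP 10.2.2).

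For a non-serious AE, the available text provides for eCRF entry and monitoring against source (Protocol 5.7 and 14.2) but gives no reporting deadline.

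**The case against.** The strongest reply is that the exclusion concerns forms of care, not kinds of event. On that view it says only that an emergency visit is not an admission and that an elective admission does not count. The medically important item stays in the list, the paragraph just before the exclusion explains it, and the incapacity item is also independent of admission. Either the investigator or the sponsor may judge an event serious, so a site's literal reading is not final. This is a fair account of the probable intent, and it rules out any claim that the criterion has been abolished. It does not remove the conflict, because the words do not express that intent. The sponsor can correct a site only after it learns of the event, and the 24-hour clock that would tell it runs only for SAEs.

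A reader might infer three stronger things, and the documents support none of them.

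- *That the exclusion hides sight-threatening risks the protocol itself attributes to the study drug.* Protocol 3.2, under limitations of existing treatments, does name "risk of angle-closure glaucoma due to activation of the ciliary muscle; and risk of retinal detachment in subjects with high myopia", but as limitations of the approved 1.25% pilocarpine product. The study uses 0.4%. Table 4 in Protocol 5.4.1 describes pilocarpine as contracting the ciliary muscle, so an extension to 0.4% is an understandable inference from the shared ingredient, but it is an inference. The documents also do not say how such events would be managed. The contradiction holds for any medically important event and does not need this example.
- *That such events would vanish from the safety results.* As TEAEs they would still be tabulated by preferred term. Only the serious count and the speed of reporting are exposed.
- *That a rate or confidence bound can be put on the loss.* A bound computed from the arm size says nothing about how often sites would misclassify.

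**Conclusion.** The rule is wrong as written: two adjacent paragraphs of Protocol 9.3.1 give incompatible answers for the same event, and the documents do not say which governs. The consequence is conditional. It requires a medically important event, treated as an outpatient emergency without admission, at a site that takes the exclusion literally and is not corrected by the sponsor. Where those conditions meet, the event loses 24-hour reporting and its place in the serious-TEAE table, but keeps its AE record and its place in the general TEAE tables. No misclassified event is shown, and the size cannot be estimated from the documents.

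No endpoint, alpha level or power is affected. This is a drafting contradiction in a safety-reporting rule. It is worth correcting because of what the label controls and because correction costs almost nothing, but it does not undermine the trial's conclusions.

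**What to change.** Reconcile the two paragraphs of Protocol 9.3.1 by limiting the exclusion to the hospitalization criterion. Suggested wording: *Outpatient emergency treatment does not by itself meet the hospitalization criterion; an event that meets any other seriousness criterion remains an SAE.* The elective and preplanned hospitalization clause can stand as a separate sentence, so that its qualifier clearly belongs to it alone. Send sites a short memo with the clarified rule.

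If enrollment has already ended, review the recorded AEs that were treated as outpatient emergencies against all the seriousness criteria, while the data are still masked, and correct the seriousness field where needed.

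The cost is one sentence in an amendment, a site memo and possibly a few more SAE forms. A pre-specified list of ocular events to be treated as medically important is optional. The protocol leaves that to medical judgment, and the contradiction can be resolved without such a list.
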